5.3 LIFESTYLE CONSIDERATIONS

There are no known normal range lifestyle considerations that could impact treatment efficacy of I-ACQUIRE other than non-compliance with the treatment protocol. This will be monitored daily during the month of treatment.

5.4 SCREEN FAILURES

Screen failures are defined as participants who consent to participate in the clinical trial but are not subsequently randomly assigned to the study intervention or entered in the study. A minimal set of screen failure information is required to ensure transparent reporting of screen failure participants, to meet the Consolidated Standards of Reporting Trials (CONSORT) publishing requirements and to respond to queries from regulatory authorities. Minimal information includes demography, screen failure details, and eligibility criteria.

Individuals who do not meet the criteria for participation in this trial (screen failure) may be rescreened at a time when they may meet enrollment criteria (e.g., infant had become ill at time when treatment was scheduled or an unexpected event prevented parents from fulfilling their role in the parent training component). Infant can be rescreened when he or she recovers, or family can fulfill inclusion criteria for participation. Rescreened participants should be assigned the same participant number as for the initial screening.

5.5 STRATEGIES FOR RECRUITMENT AND RETENTION

We will recruit 240 families who complete baseline assessments from 12 or more sites. Eligible children will include those known to the sites (from clinical databases, direct care, and satellite sites) and those recruited from other hospitals, clinics, and early intervention programs. Each site will compile an inventory of regional sources to distribute recruitment materials, using locally-adapted print materials, posters, media announcements, and web-based study information. Also, we will use 2 approaches that have successfully recruited subjects in our other multi-site studies - social media and advocacy groups. Finally, we will list the trial on *ClinicalTrials.gov*, which has generated volunteers who re-locate temporarily for treatment and agree to travel for all scheduled assessments. We will assist these families in finding low- or no-cost housing options, if requested. The I-ACQUIRE Clinical Trial website will have recruitment materials for families and clinicians in English (with a notation that at least one parent must be proficient in English). Recruitment materials and methods will be finalized jointly with the Parent Council (see below) with a clear goal of recruiting a representative and racially/ethnically diverse sample.

6 STUDY INTERVENTION

6.1 STUDY INTERVENTION(S) ADMINISTRATION

6.1.1 STUDY INTERVENTION DESCRIPTION

OVERVIEW OF CORE TREATMENT COMPONENTS FOR I-ACQUIRE (BOTH DOSES)

1. Constraint of the child's less-impaired upper extremity for first 17 days of treatment; cast is worn 24/7. Children will continuously wear a full-arm lightweight cast for the first 17 of 20 therapy sessions. The cast is made from focus rigidity casting material with arm and hand positions specified and uni-valved for easy removal weekly for safety checks. For the last 3 treatment days, the therapist removes the cast and focuses on integrating the new skills of the hemiparetic UE into bimanual activities. Constraint is designed to reduce competing sensory-motor input and consistently help direct the child's attention to use of the hemiparetic arm/hand.

2. High dosage of treatment – either 3 or 6 hrs/day, 5 days/wk for 4 weeks. (see above for rationale in choosing these dosages). CIMT is premised on evidence that concentrated high amounts of shaping and varied practice of new skills can produce rapid and enduring improvements in UE skills and functional use. A protocol-trained therapist provides 20 treatment sessions of either 3 or 6 hrs/day, 5 days/wk X 4 wks. Therapists are scheduled to have an extra hour each day to cover child naps and breaks (which are not included in daily documentation of time spent in active therapy). We re-affirm that young children have tolerated both dose levels well, largely because of therapists' skills in maintaining high infant interest and enjoyment and frequent shifts in the therapy activities. (See Prior Studies.)

3. Operant conditioning techniques to shape and improve upper extremity (UE) skills; combined with practice variation. Operant conditioning is applied across a wide range of activities with the goal of eliciting new UE skills and then improving voluntary motor control by progressing through a cycle in which specific verbal, visual, and/or physical requests for a movement or behavior are made, often with the therapist modeling and prompting, particularly at early stages. The methods for setting behavioral goal standards, providing rewards, and then increasing levels of consistent performance required to earn continued reinforcement are

described in detail in the ACQUIREc administration manual¹⁶ and training materials. We term this the MR3 Cycle (**m**ovement, **r**einforcement, **r**epetition, and **r**efinement).¹⁶ Activities are varied, game-like, and enjoyable for the infant; self-help activities provide frequent natural opportunities for the MR3 cycle.

4. Provision of therapy in natural settings. We provide therapy in natural environments, because this promotes generalization and maintenance of skills. For young children, this can include varied environments such as the home, childcare, or early intervention settings. Sometimes clinic settings can be set-up to be similar to home or childcare settings. Parents and family members often are present and join in some therapy activities.

5. Emphasis on total body and bimanual activities (as well as traditional arm/hand therapy activities)
Treatment activities extend to total body and gross motor activities that use the hemiparetic UE, e.g., sitting with stability, weight bearing, rolling, scooting, standing, crawling, and walking. Even with the cast, many gross motor bimanual activities can occur during treatment, e.g., crawling, rolling, carrying, pushing, or pulling large object).

6. Home Treatment Module developed as an active Parent-Therapist Partnership. We developed and use a parent-home training module (with supportive written materials and photo/videotapes). The therapist and parents meet at the beginning of treatment and at least weekly for 4 weeks. Initially, the therapist coaches the parent in the I-ACQUIRE processes, particularly concerning effective and ineffective use of operant conditioning. Parents help identify goals, introduce new activities, and help tailor therapy activities to promote the use of newly acquired skills in many different situations. Expectations are that parents enact their component for about 45 min per day on 5 of 7 days. (This can be divided into shorter times and include mother and/or father engagement. It is acceptable if only one parent provides the home program.) Daily review by therapists and parents of individualized home-based activities includes child responses and time spent and promotes two-way benefits for the child's treatment. Parents and therapists complete the Parent-Therapist Relationship Tool at the end of treatment week 4.

7. Documentation of daily therapy sessions. Each therapist documents treatment with standardized daily logs that record treatment goals worked on, activities completed (divided into discrete skills and levels), infant behavior (interest level, signs of frustration or fatigue), and any progress or decline. I-ACQUIRE protocol recommends that the therapist vary the therapy activities or stop therapy (within a session or overall) if unexpected problems occur, such as high levels of infant distress (lasting more than 3 minutes). If needed, the therapist may obtain consultation from senior I-ACQUIRE therapists at the Treatment Implementation Core about the course of treatment.

8. Transfer Package to promote future progress. Therapist and parents develop a written plan with extensive supportive materials to help the child maintain and improve skills post-treatment. This plan targets every day and special activities, informed by the overall treatment process, how the child has progressed across various skill levels, and next steps towards higher level functional use.

6.1.2 DOSING AND ADMINISTRATION

In the primary Phase 1, all participants will be randomly assigned to one of the 3 groups. Two pre-determined dosages of I-ACQUIRE are implemented as part of the study design. In the crossover Phase 2, for children assigned initially to Group 3, Usual and Customary Treatment, their parent(s) may consent for the child to be randomized to Moderate or High Dose I-ACQUIRE and then be assessed at the end of treatment and 6 mos post-treatment. Note: the crossover Phase 2 data will not be used to test the primary trial hypotheses about efficacy of the two dosages of I-ACQUIRE compared to Usual and Customary Treatment and to each other.

6.2 PREPARATION/HANDLING/STORAGE/ACCOUNTABILITY

6.2.1 ACQUISITION AND ACCOUNTABILITY

At the Post-Treatment Assessment visit, after obtaining parental consent for DNA collection, the blinded assessor will collect a DNA sample from the child by gently rubbing the inside of the child's cheeks with two small, soft tipped, Oragene brushes. These have been successfully used by our collaborators in other genetic studies. In 1 out of 4 children we will likely need to collect a second sample, because of insufficient saliva or other problems with the quality of biological material collected. This repeat data collection will occur at the 6 mos. Post-Treatment Assessment.

6.2.2 FORMULATION, APPEARANCE, PACKAGING, AND LABELING

Not Applicable

6.2.3 PRODUCT STORAGE AND STABILITY

Not Applicable

6.2.4 PREPARATION

The two swabs will be sent to a central Yale University laboratory where the DNA will be stored, extracted, and analyzed for single nucleotide polymorphism expression.

6.3 MEASURES TO MINIMIZE BIAS: RANDOMIZATION AND BLINDING

Subjects will be randomized in a 1:1:1 fashion to U&CT, Moderate Dose I-ACQUIRE, or High Dose I-ACQUIRE using a restricted randomization algorithm which controls for within site treatment imbalances. If no imbalances exceed the tolerated threshold, the patient is randomized according to the specified allocation ratio (1:1:1) using a block urn design. If an unacceptable level of imbalance exists, the algorithm will determine whether the current allocation ratio improves or exacerbates the current imbalance and adjust the ratio accordingly. The detailed randomization scheme and source codes will be provided in the Randomization Plan document. Note: for general understanding, the randomization process will be described in the consent document for parents as having an equally fair chance of being assigned to one of the 3 treatment groups.

Upon confirmation of eligibility and obtaining parental permission to participate, study coordinators will log into the WebDCU™ study database and receive the computer-generated randomization assignment. Local Site Coordinators will notify families promptly to schedule baseline assessments and designate the treatment month.

It is not possible to blind the family or the treatment team; however, no treating therapist will conduct assessments for primary and secondary outcomes, and none of the blinded assessors will work in the same setting as treatment staff. In addition, the primary and secondary outcomes will be coded by staff at the Central Assessment Core at The Ohio State University, remote from the clinical site and treatment implementation core. Assessment Core research staff will be blinded to treatment and the videos will be randomly sorted so that central coders cannot know whether a video is the baseline or one of the follow-up assessments. Parents also are reminded before each assessment session not to discuss their child's treatment with the assessor.

For assessments completed by the local blinded assessor, a second blinded scoring will be calculated by the central blinded assessment team if the local assessor has indicated that he or she possibly has become unblinded. Only blinded scores will be used in the primary analysis, but sensitivity analyses will compare the local and central scores to assess for any potential differences due to the unblinding.

6.4 STUDY INTERVENTION COMPLIANCE

We will define I-ACQUIRE treatment compliance as: (1) receiving therapy on at least 17 of the 20 intended days; (2) receiving the full daily dosage \pm 30 minutes on at least 15 treatment days; (3) wearing the cast continuously on at least 15 treatment days and over the weekends (NB: the cast is removed for the final 3 days of therapy intentionally to provide 3 sessions focused on bimanual activities); (4) the parent received training in the home-based component and provided evidence that this occurred on at least 12 days over the 4 wk treatment period; (5) completion of treatment occurs within 5 weeks of the first treatment session (this allows for a brief extension in the 4-wk treatment in the event of a short disruption, such as an illness, minor injury (not treatment-related), or family problem). We will examine the proportion of subjects in each I-ACQUIRE treatment group who did not receive this minimum level of treatment (i.e., met these criteria for treatment compliance) and seek to understand the likely reasons for non-compliance.

Whenever we restrict the analytic sample to the as-treated sample, we will report the number and characteristics of subjects who differ in treatment compliance (Moderate and High Dose I-ACQUIRE) or in distinct U&CT care subtypes (e.g. type of therapy, categorized treatment durations), and will consider if the final as-treated and Modified ITT samples differ in their sociodemographic or clinical characteristics. This is important so that study findings obtained from any as treated sample analyses can specify whether the results apply to the entire patient population or only to certain subgroups.

6.5 CONCOMITANT THERAPY

Not Applicable

6.5.1 RESCUE MEDICINE

Not Applicable

7 STUDY INTERVENTION DISCONTINUATION AND PARTICIPANT DISCONTINUATION/WITHDRAWAL

7.1 DISCONTINUATION OF STUDY INTERVENTION

Study intervention would be discontinued for an individual subject if a serious adverse event (SAE) related to the trial occurs, if an SAE unrelated to the trial occurs that in the opinion of the site investigator will preclude safe participation in the rest of the trial, or if the futility analysis (see full statistical plan for details) deems the treatment highly unlikely to be worthy of continued study.

Note: a short-term disruption or discontinuation of the study intervention could occur due to unforeseen health, safety, or family issues. If these occur, we would discuss this with parents and seek a resolution to the problem. If these necessitate any change to the overall study protocol or procedures, we would notify the CIRB to discuss and consider any options. (In the past, for example, a family emergency could arise and cause a re-scheduling of a treatment session on the weekend, or a sudden onset of a short-term illness in the child, parent, or even therapist could lead to a re-scheduling of an assessment session that has begun, or a treatment session. Typically, these lead to a minor schedule adjustment. This does not lead to dropping a participant from the study or future follow-up assessments.)

7.2 PARTICIPANT DISCONTINUATION/WITHDRAWAL FROM THE STUDY

Participants are free to withdraw from participation in the study at any time upon request.

- The reason(s) for participant discontinuation or withdrawal from the study will be recorded.

7.3 LOST TO FOLLOW-UP

A participant will be considered lost to follow-up if he or she fails to return for scheduled post-treatment assessments, and/or is unable to be contacted by the study staff.

The following actions must be taken if a participant fails to return for a required study visit:

- The study team will attempt to contact the participant's parent(s) and reschedule the missed visit and counsel the parent on the importance of maintaining the assigned visit schedule.
- Before a participant is deemed lost to follow-up, the investigator or designee will make every effort to regain contact with the parent(s) of the participant (when possible, 3 telephone calls and email communications and, if necessary, a certified letter to the participant's last known mailing address or local equivalent methods). These contact attempts should be documented in the participant's study file.
- Should the participant continue to be unreachable, he or she will be considered to have withdrawn from the study with a primary reason of lost to follow-up.

8 STUDY ASSESSMENTS AND PROCEDURES

8.1 EFFICACY ASSESSMENTS

Primary Outcome MEASURE: The Emerging Behaviors Scale (EBS). The EBS is a standardized tool developed for pediatric rehabilitation research in hemiparesis. The rationale for this tool is that all young children, including those with hemiparesis, need to acquire a repertoire of essential upper extremity (UE) skills that are used frequently every day during play, self-help, object manipulation, and social communication. Without a sufficient number of these critically important UE skills, a child's future progress will be delayed and will lead to increasing impairment over time. The EBS thus represents a foundational base of core UE skills that extend into later ages. The EBS tallies the number of core skills (0 to 30) with the hemiparetic UE. (Note: once an infant acquires an early version of each skill, therapy focuses on improving that skill – e.g., ease, accuracy, speed, and integration with other skills into complex sequences). Items on the EBS appear as part of standardized tools (e.g., Bayley-4, Peabody Scales of Motor Development-2, the QUEST, NIH Toolbox). A unique feature of the EBS is the requirement that the child display each skill at least twice. Coding is completed by the blinded Central Assessment Core staff based on the videotaped session that includes the full Bayley-4, the Mini AHA, a snack break, and interactions with the assessor and parent at the start and close of the session. The parent ratings on the IMAL can be used as a source of one of the two times the skill was documented. All EBS items have high face and content validity and inter-rater reliability established on at least 3 standardized tools. Most have high predictive validity for the child's future performance on the same or similar items.

The primary efficacy outcome is defined as gaining and retaining ≥ 7 new EBS skills above baseline EBS score at the End of Treatment and 6 mos Post-Treatment Assessments. Rationale and supportive evidence for the proposed criteria for a minimal clinically important outcome: For the past several years, we have engaged in efforts to identify a minimal clinically meaningful improvement on the EBS. We have reviewed outcomes for subjects in prior trials and our clinical database; studied clinical thresholds in other rehabilitation trials and goal-setting in therapy (often 5 – 10% gains); obtained input from pediatric OTs, PTs, and physiatrists; compared several thresholds that vary for subject age or baseline score; and cross-checked EBS scores with parent ratings, observations, and therapist logs of child progress

We recognize that a single dichotomous primary outcome has limits – notably, reduced detail about the precise magnitude of change and its slope over time. Finally, we selected the dichotomous outcome because: i) we think establishing pre-specified minimum high expectation for gaining and then maintaining a large number of new skills is justified, given the high cost of this time-intensive treatment. That is, if the gains were only short-term, parents and clinicians would likely be disappointed that benefits are merely transitory; and ii) we think the dichotomous outcome is easier for clinicians and parents to understand than a distribution-based or individualized outcome that is difficult to understand (because the EBS tool itself and the meaning of the range of scores are not widely known). The threshold of gaining ≥ 7 new EBS skills can be equated with about one-fourth of the entire EBS repertoire; further, all infants in the I-ACQUIRE trial and most infants with PAIS will have baseline EBS scores that allow them to acquire this many new skills. Our analyses affirm that this simple,

dichotomous outcome works well across the entire EBS continuum to classify those with and without a favorable treatment outcome. In our earlier studies, patients with divergent EBS baselines showed mean EBS gains ≥ 7 new skills. We are not certain, however, that a gain of only 6 EBS skills has no clinical meaning to an infant or parents.

We further note that children with a baseline EBS of 24 or higher are excluded from the trial in terms of testing the primary efficacy outcome, because this would preclude achieving the study threshold. (Based on prior clinical trials and clinical research, a baseline EBS score of 24 or higher would be extremely rare. We further note, however, that we think the I-ACQUIRE treatment could possibly result in meaningful improvement for such a high functioning child, although the choice of the EBS as the primary outcome measure does not allow for fully capturing such potential benefits.)

Secondary Outcome MEASURE: The Mini-Assisting Hand Assessment (Mini AHA). The Mini AHA is a new tool that rates how well a child engages the hemiparetic UE as a “helper” in bimanual activities, recognizing that children with hemiparesis are unlikely to use their hemiparetic UE as their dominant E. The Mini AHA has high inter-rater reliability. A Rasch measurement analysis supports inter-scale validity, showing items fit well with underlying constructs and a developmental model. A Pearson Separation ratio of 9.67 affirms children can be reliably separated into functional levels based on scores. Note: Test developers require formal training and certification to use this tool. We sponsored the first training session in the U.S. Certified assessors score 20 items on a 4-pt scale from videotaped sessions. Raw scores are converted into unit (or logit) scores (0 to 100). Presently, there is no basis for establishing a minimal clinically meaningful threshold, thus we will use the total Mini AHA unit score.

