4 STUDY DESIGN

4.1 OVERALL DESIGN

The proposed study is a Phase III trial powered to determine efficacy of two different doses of I-ACQUIRE for children 8 to 24 months old with PAIS and hemiparesis. The design is a prospective RCT in which 240 children will be randomly assigned to one of 3 treatment groups (N=80 per group): 1) Moderate Dose I-ACQUIRE (3 hrs/day, 5 day/wk X 4 wks), 2) High Dose I-ACQUIRE (6hrs/day, 5 days/wk X 4 wks), or 3) Usual and Customary Treatment (U&CT). I-ACQUIRE will be delivered by protocol-trained therapists and monitored weekly for dosage and treatment fidelity; U&CT will be provided by community therapists with dosage and approaches documented weekly. All primary and secondary efficacy outcomes rely on blinded assessments at baseline, end of treatment, and 6 mos post-treatment. Exploratory outcomes and supplemental clinical measures may provide valuable additional data about development and health in this sample of children with PAIS.

There will be a second phase of the I-ACQUIRE Study for the children who had been randomly assigned to Group 3 (Usual and Customary Treatment). Their parent(s) may choose to enroll (via a new IRB-approved consent process) to have their child randomly assigned to receive either the Moderate or High Dose I-ACQUIRE treatment. This will occur after the 6-mos Post-Treatment Assessment from the primary phase. Outcome data from this second or crossover phase of the study will not be used in the primary data analysis for this trial but will be available for exploratory and post hoc data analyses.

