Additional descriptive measures (not blinded) and rationale for collecting. We value the perspectives of parents about their children's response to treatment and their observations of their child's development. Parents have the greatest amount of experience with their child. They uniquely can provide ratings about what they observe in terms of their child's use of the hemiparetic UE in everyday settings and their participation in a wide variety of age-appropriate activities. Accordingly, parents will complete the Infant Motor Activity Log (IMAL),²⁶ a standardized tool about "how well" and "how often" their child uses the hemiparetic UE in 20 everyday behaviors (e.g., holding bottle/cup, eating finger foods, pushing a button, reaching to be picked up). The scale is 0 to 5 with behavioral anchoring provided. The IMAL will provide useful descriptive information to accompany the findings about primary and secondary efficacy. Parents also will complete the MacArthur-Bates Communicative Development Inventories (CDI),¹³⁰ a standardized reliable tool to assess the child's communicative competence. There is an infant version for 8 to 18 mos and a toddler version for 18 to 30 mos which can be used for older children who have shown language delay. Previous clinical observations of children treated with I-ACQUIRE indicate that children's language abilities may be improved by the treatment. Theoretically, this is important to understanding neuroplasticity and cross-domain changes after treatment. Parents also complete the Perceived Stress Scale at each assessment to monitor for parent response to treatment group and answer questions about their perceptions of their child's stress levels.

Clinical data about the infants: A Pediatric Neurology Exam will occur at each site at baseline by a trial-affiliated pediatric neurologist or physiatrist. It will include the Pediatric Stroke Outcome Measure (PSOM) (severity scores from 0 to 10), and information about co-morbidities, general health and health history, and the child's current and past treatments. These data will be used to describe the clinical sample and to compare subjects across treatment conditions and clinical sites.

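### Unblinded parent ratings can supply one of the two displays that credit a skill on the primary endpoint (EBS), which conflicts with the statement that all primary outcomes rest on blinded assessment

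*Protocol*

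**What the plan says.** Section 8.1 defines how the primary outcome is scored. The two-display rule is stated first: "A unique feature of the EBS is the requirement that the child display each skill at least twice". The coding is blinded and central: "Coding is completed by the blinded Central Assessment Core staff based on the videotaped session". The next sentence opens a second source: "The parent ratings on the IMAL can be used as a source of one of the two times the skill was documented".

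Elsewhere the protocol describes that source as unblinded and descriptive. Section 6.3 says: "It is not possible to blind the family or the treatment team". Section 8.2 introduces the IMAL under the label "Additional descriptive measures (not blinded) and rationale for collecting" and gives its role: "The IMAL will provide useful descriptive information to accompany the findings about primary and secondary efficacy".

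The general claim about outcomes is in section 4.1: "All primary and secondary efficacy outcomes rely on blinded assessments at baseline, end of treatment, and 6 mos post-treatment". Section 6.3 adds: "Only blinded scores will be used in the primary analysis". That last sentence stands in a paragraph about local assessors who may have become unblinded, so it is not written as a rule about EBS inputs.

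Section 6.1.1 (item 6) describes a home module for both I-ACQUIRE doses. The therapist coaches the parent initially, they meet at least weekly, and the parent is expected to deliver about 45 minutes of home therapy on 5 of 7 days. No such module is described for U&CT.

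**The concern.** The primary endpoint is a hard cut-off, a gain of at least 7 EBS skills at both follow-up assessments, so one or two items can decide whether a child is a responder. If some items are credited partly on the rating of a parent who knows the assignment, the EBS total is not a fully blinded score. Parents in the I-ACQUIRE arms have been coached and have worked daily on hand skills, and U&CT parents have had nothing comparable. Their ratings may therefore differ for reasons other than the child's ability.

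An error that differs by arm would bias the comparison of each dose with U&CT, and a larger sample would not remove it. The safeguards in section 6.3 (remote coding, random sorting of videos) protect only what is on the video. The sensitivity analysis there compares local with central scores, and the continuous-EBS analysis in section 9.4.2 uses the same EBS. Neither would separate IMAL-credited items from items seen twice on video.

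**Working it through.** **1. The text.** Sections 8.1 (parent rating may count), 6.3 (parents unblinded), 8.2 (IMAL unblinded and descriptive) and 4.1 (all primary outcomes blinded) cannot all hold for one score. No section describes an EBS scored without the IMAL, or says which IMAL rating (0 to 5) counts as a display.

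**2. What is exposed.** The IMAL supplies at most one of two displays, so on the text the other should come from the blinded video. Only skills seen exactly once on video are at risk. The IMAL has 20 behaviours and the EBS 30 skills. Their overlap is not given.

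**3. The plan's own sample size.** Inputs from section 9.2: 70% vs 40%, two-sided 5%, 90% power.

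n = [1.960·√(2·0.55·0.45) + 1.282·√(0.21 + 0.24)]² / 0.30² = (1.379 + 0.860)² / 0.09 ≈ 55.7, so 56 per group against the stated 57. Then 57 × 1.39 = 79.2, rounded up to 80 per group and 240 in total. The plan's figure reproduces, and 80 per arm is used below.

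**4. Illustration of consequence.** The protocol gives neither the SD of EBS gain nor the amount of IMAL credit, so both are assumed. Let d be the net average inflation of gain in an I-ACQUIRE arm relative to U&CT, acting at both follow-up assessments. With roughly normal gain,

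success rate = Φ(Φ⁻¹(p) + d/SD), SD = 4, 5, 6.

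For p = 15% (the U&CT figure in section 9.2), Φ⁻¹(0.15) = −1.036. With d = 1 and SD = 5 the rate is Φ(−0.836) = 20.1%.

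Take 15% as the true rate in all arms, 80 per arm and a pooled two-proportion test at two-sided 5%. *Ungated* is one dose against U&CT alone. *Gated* also requires the three-group test (Pearson chi-square, 2 df, at 5%) to reject first, as section 9.4.1 demands, with both doses shifted by d.

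| d (skills) | Apparent success, SD 4 / 5 / 6 | Ungated | Gated |
|---|---|---|---|
| 0 | 15% | about 5% | about 2.4% |
| 0.5 | 18.1 / 17.5 / 17.0% | 8.0 / 6.8 / 6.2% | 4.4 / 3.6 / 3.2% |
| 1 | 21.6 / 20.1 / 19.2% | 18.8 / 13.4 / 10.7% | 11.9 / 8.1 / 6.2% |
| 2 | 29.6 / 26.2 / 24.1% | 61 / 42 / 31% | 52 / 32 / 22% |

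The ungated column is computed from the binomial distributions, the gated one by simulation. The gated figures should be read against the gated no-bias value of about 2.4%, not against 5%.

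**5. High versus Moderate Dose.** The parent module is common to both. Shifting both by one skill moves 40% to 47-50% and 70% to 76-78%. The planned 30-point difference becomes 28 to 29 points (for SD 4, 78.1 − 49.9 = 28.2). The error largely cancels here.

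**6. Inflation at one visit only.** If a one-skill inflation affects End of Treatment alone, the two-visit requirement limits the rise from 15% to about 17-18% (assumed between-visit correlation 0.5 to 0.8).

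**The case against.** The strongest reply is that the route is narrow. Blinded central staff do the coding without knowing which visit a video shows, and a parent can add only the second display. The number of IMAL behaviours that match EBS skills may be small, and over-rating common to all three assessments would partly cancel in a gain score. Nothing in the documents supports a net inflation as large as one or two skills. The parent rating also has a purpose: a toddler may not show a skill twice in one session, and dropping the IMAL will lose some true skills. The Mini AHA, scored by certified assessors from video, gives a check free of parent ratings.

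All of this stands as a limit on size. It does not reconcile sections 4.1 and 8.1, and it does not separate the affected items from the rest.

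A reader might infer more than the documents support:

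- **That parents alone can create an EBS skill.** The text allows them one of two displays.
- **That I-ACQUIRE parents are trained every week to notice EBS items.** Section 6.1.1 has weekly meetings and initial coaching, and mentions neither noticing nor EBS items.
- **That randomization before baseline makes the bias worse.** Section 6.3 places assignment before baseline, so parents may know the arm by then, but the text does not say so or give the timing of the IMAL. Over-rating at baseline would reduce the gain and only under-rating would inflate it.
- **That the trial's type I error is 11-19% or higher.** That is an ungated, conditional figure for an assumed full skill of net inflation.

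**Conclusion.** The point holds as a conflict in the definition of the primary outcome and as an open route for unblinded error. It concerns each dose against U&CT and should matter little for High against Moderate Dose. The direction favouring I-ACQUIRE is plausible because only those parents are coached and deliver home therapy, but neither direction nor size can be established from the protocol. The type I error figures rest on an assumed SD of gain of 4 to 6, roughly normal gain, true success of 15% throughout, 80 per arm, and a net inflation present at both follow-up assessments. At a net half skill, the gated error stays below the nominal 5%. Confidence is high on the textual conflict and low on the magnitude. It merits correction because it sits in the primary endpoint and a specific change removes it.

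**What to change.** In section 8.1, state that the EBS used for the primary endpoint is scored at baseline, End of Treatment and 6 months from the blinded video only, with both displays on video. Report the IMAL-assisted EBS as a labelled sensitivity analysis. Bring sections 4.1, 6.3, 8.1 and 8.2 into line with that rule.

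If the sponsor keeps the IMAL-assisted score as primary, prespecify the video-only EBS as a sensitivity analysis, and stop describing the primary outcome as fully blinded.

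Costs: some true skills shown once in a session are lost, so EBS totals and possibly response rates fall. The 7-skill cut-off and the planning rates of 70%, 40% and 15% are not shown to hold under video-only scoring. For assessments already coded, re-derivation is simple if the source of each display was recorded. If it was not, the stored videos must be recoded.
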